6.1.3. Analysis of Secondary Efficacy Endpoints

6.1.3.1. Analysis of the Proportion of Subjects with HIV-1 RNA ≥ 50 copies/mL at Week 26 as determined by FDA-defined Snapshot Algorithm

The analysis of the proportion of participants with HIV-1 RNA ≥ 50 copies/mL at Week 26 as determined by the US FDA-defined snapshot algorithm will be based on the FAS.

A supportive analysis based on the PP analysis set will also be performed. Participants excluded from the PP analysis set will be determined before database lock.

6.1.3.2. Analysis of the Proportion of Subjects with HIV-1 RNA < 50 copies/mL at Week 26 as determined by FDA-defined Snapshot Algorithm

Proportion of subjects with HIV-1 RNA < 50 copies/mL at Week 26 as determined by US FDA-defined snapshot algorithm will be analyzed based on the FAS and the PP analysis sets, similar to the efficacy endpoint of proportion of subjects with HIV-1 RNA ≥ 50 copies/mL at Week 26 as determined by FDA-defined Snapshot Algorithm.

6.1.3.3. Analysis on CD4+ Cell Counts at Week 26

The changes from baseline in CD4+ cell count at Week 26 will be summarized by treatment group and overall for FAS using descriptive statistics. The change from baseline in CD4+ cell

count will also be summarized for other visits up to Week 26 for the LA Regimen Period Analysis, and up to Week 52 for the Whole Study Period Analysis.

The absolute values of CD4 cell counts will be also summarized by treatment group and overall similarly. The analyses of CD4 cell counts and their changes from baseline will be conducted using the FAS.

The mean and 95% CI of change from baseline in CD4+ cell count over time by treatment groups and overall will be plotted for the FAS.

CD4+ cell counts over time in individual participants will be plotted by treatment groups.

6.2. Other Efficacy Endpoints

6.2.1. Definition of Other Efficacy Endpoints

- The proportion of participants with HIV-1 RNA < 50 copies/mL at Week 26 as defined by 2 different missing data imputation methods specified in Section 6.2.2.1.
- The change from baseline in CD4 percentage (%), CD8 count, and CD4/CD8 Ratio at Week 26.

6.2.2. Analysis of Other Efficacy Endpoints

6.2.2.1. Analysis of Proportion of Participants with HIV-1 RNA < 50 copies/mL by Missing = Failure and Missing = Excluded Approaches

Number and percentage of participants with HIV-1 RNA < 50 copies/mL by visit will be analyzed using the following 2 methods for imputing missing HIV-1 RNA values.

- Missing = Failure (M = F):
In this approach, missing data will be treated as virologic failure and summarized into the “missing” category (see list of HIV-RNA categories below).
- Missing = Excluded (M = E):
In this approach, missing data will be excluded in the computation of the percentages (ie, missing data points will be excluded from both the numerator and denominator in the computation). The denominator for percentages at a visit is the number of participants in the FAS with nonmissing HIV-1 RNA value at that visit.

For both M = F and M = E analyses, the number and percentage of participants with HIV-1 RNA in the following categories will be summarized by treatment group and total for Week 26 and other visits up to Week 26 for the LA Regimen Period Analysis, and up to Week 52 for the Whole Study Period Analysis based on the FAS:

- < 50 copies/mL
 - < 20 copies/mL
 - < 20 copies/mL Not Detectable
 - < 20 copies/mL Detectable
 - 20 to < 50 copies/mL
- 50 to < 200 copies/mL
- 200 to < 400 copies/mL
- 400 to < 1000 copies/mL
- ≥ 1000 copies/mL
- Missing (only applicable to M = F analysis)

The proportion of participants with HIV-1 RNA < 50 copies/mL as defined by the 2 different missing data imputation methods will be analyzed using the same statistical method applied to the secondary efficacy endpoint.

For the M = F analysis, the proportion of participants with HIV-1 RNA < 50 copies/mL will be plotted by treatment group for all visits up to Week 26 for the LA Regimen Period Analysis, and up to Week 52 for the Whole Study Period Analysis using the FAS.

6.2.2.2. Analysis of CD4 Percentage, CD8 Count, and CD4/CD8 Ratio

The change from baseline in CD4 percentage (%), CD8 count, and CD4/CD8 ratio will be based on the FAS and summarized for Week 26 and other visits up to Week 26 for the LA Regimen Period Analysis, and up to Week 52 for the Whole Study Period Analysis using descriptive statistics.

6.3. Changes from Protocol-Specified Efficacy Analyses

The definition of Full Analysis Set (FAS) is defined differently from the Protocol. Exclusion of participants who have major protocol violation (defined as meeting exclusion criterion of having chronic hepatitis B virus [HBV] infection) from the Full Analysis Set has been added in the SAP.

7. SAFETY ANALYSES

The primary objective of this study is to evaluate the safety and tolerability of a combination of the bNAbs GS-5423 and GS-2872 in combination with the HIV capsid inhibitor LEN, and the primary endpoint of this study is incidence of treatment-emergent SAEs through Week 26. The second endpoint of this study includes incidence of treatment-emergent AEs through Week 26.

Safety data will be summarized for participants in the Safety Analysis Set for the whole study period analysis and for participants in the Safety Analysis Set for LA regimen period analysis, separately, unless otherwise specified. All collected data will be included in data listings.

7.1.1. Adverse Event Dictionary

Clinical and laboratory AEs will be coded using the current version of the Medical Dictionary for Regulatory Activities (MedDRA). System organ class (SOC), high-level group term (HLGT), high-level term (HLT), preferred term (PT), and lower-level term (LLT) will be provided in the AE dataset.

7.1.2. Adverse Event Severity

Adverse events are graded by the investigator as Grade 1, 2, 3, 4, or 5 according to toxicity criteria specified in the protocol. The severity grade of events for which the investigator did not record severity will be categorized as “missing” for tabular summaries and data listings. The missing category will be listed last in summary presentation.

7.1.3. Relationship of Adverse Events to Study Drug

Related AEs are those for which the investigator selected “Related” on the AE eCRF to the question of “Related to Study Treatment.” Relatedness to each study drug is justified by investigator and recorded on AE eCRF, for example, relatedness to Oral LEN is which investigator selected “Related” on the AE eCRF to the question of “Related to Study Treatment Oral LEN”. Relatedness will always default to the investigator’s choice, not that of the medical monitor. Events for which the investigator did not record relationship to study drug will be considered related to study drug for summary purposes. However, by-participant data listings will show the relationship as missing.

7.1.4. Serious Adverse Events

Serious adverse events (SAEs) will be identified and captured as SAEs if the AEs met the definitions of SAEs that were specified in the study protocol. SAEs captured and stored in the clinical database will be reconciled with the SAE database from the Gilead Global Patient Safety (GLPS) Department before data finalization.

7.1.5. Treatment-Emergent Adverse Events

7.1.5.1. Definition of Treatment-Emergent Adverse Events

Treatment-emergent AEs (TEAEs) are defined as follows:

- Any AEs leading to premature discontinuation of study drug, or
- Any AEs with an onset date on or after the study drug start date and
 - (i) prior to the last exposure date of LA Regimen Period for the LA Regimen Period Analysis
 - (ii) no later than the last exposure date for the Whole Study Period Analysis.

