8.1.2. Primary Endpoint

The primary endpoint of this study is as follows:

- Incidence of treatment-emergent SAEs through Week 26

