8.6.2. Adverse Events

Clinical and laboratory AEs will be coded using the Medical Dictionary for Regulatory Activities (MedDRA). System organ class (SOC), high-level group term (HLGT), high-level term (HLT), preferred term, and lower-level term (LLT) will be attached to the clinical database.

Events will be summarized on the basis of the date of onset for the event. Any treatment-emergent AEs will be defined as any AE that begins on or after the date of first dose of study drug up to the end of the protocol-defined follow-up period. For participants who discontinue from only the oral LEN, only AEs collected up to 60 days after the last dose date will be considered treatment-emergent.

Summaries (number and percentage of participants) of treatment-emergent AEs (by SOC and preferred term) by treatment group will be provided. Additional summaries will include summaries for AEs by grade, investigator's assessment of relationship to study drug, and effect on study drug dosing.

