3. GENERAL CONSIDERATIONS FOR DATA ANALYSES

Analysis results will be presented using descriptive statistics. For categorical variables, the number and percentage of participants in each category will be presented; for continuous variables, the number of participants (n), mean, standard deviation (SD) or standard error (SE), median, first quartile (Q1), third quartile (Q3), minimum, and maximum will be presented.

By-participant listings will be presented for all participants in the All Randomized Analysis Set and sorted by participant identification (ID) number, visit date, and time (if applicable). Data collected on log forms, such as AEs, will be presented in chronological order within the participant. The treatment group to which participants were randomized will be used in the listings. Age, sex at birth, race, and ethnicity will be included in the listings, as space permits.

There are the following 2 sets of analyses defined for this study. Data included in each analysis are defined as follows:

Long Acting (LA) Regimen Period Analysis

Long-acting (LA) Regimen Period Analysis includes efficacy (ie, HIV-1 RNA and CD4 cell count and percentage) and safety data collected during **Long Acting Regimen Period** from participants randomized and received at least one dose of the complete long acting study drug regimen (ie, SC LEN + GS-5423 and GS-2872) up to ART restart (eg, Week 26). All data collected up to the last exposure date of LA regimen (defined in Section 3.8.1) will be summarized except for data on AEs, death and concomitant medications. For AEs, death and concomitant medications, only data collected prior to the last exposure date of LA regimen will be included. For participants who did not restart ART on or before last study date or have missing ARV restart date, all data will be included.

Data included in this analysis will be used to assess the efficacy and safety data collected during the LA regimen period of the study. Results will be summarized by treatment group and overall.

Whole Study Period Analysis

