3.8.1. Definition of Key Dates and Study Day

Study Day 1 is defined as the day when the first dose of any study drug was taken, as recorded on the Study Drug Administration eCRF (ie, oral LEN, SC LEN or infusion drugs [GS-5423, GS-2872]).

Last Dose Date is defined as the latest dose date of any study drug as recorded on the Study Drug Administration eCRF (ie, oral LEN, SC LEN or infusion drugs (GS-5423, GS-2872) for participants who prematurely discontinued study drug or completed study drug according to Study Drug Completion eCRF.

Study Days are calculated relative to Study Day 1 of study drug and derived as follows:

- For postdose study days: Assessment Date – First Dose Date + 1
- For days prior to the first dose: Assessment Date – First Dose Date

Baseline Value is defined as the last value obtained on or prior to the first dose of study drug.

Last Study Date is the latest clinic visit dates, and/or the laboratory visit dates, whichever is latest, including the any follow-up visit dates, for participants who prematurely discontinued study or completed study according to the Study Completion eCRF.

Last Exposure Date is defined as follows for participants who prematurely discontinued study or complete study according to Study Completion eCRF (i.e. participant answered “No” or “Yes” for “Did the participant complete the protocol-planned duration of the study” on Study Completion form):

- For participants who receive any injection or infusion, last exposure date is defined as last study date.
- For participants who do not receive any injection or infusion (i.e. for those who only receive oral LEN), last exposure date is defined as the earliest of the last dose date plus 60 days and the last study date.

The last exposure date is defined considering the prolonged exposure of LEN, GS-5423, and GS-2872 after the last dose date of LEN, GS-5423, and GS-2872 through the end of study.

Last Exposure Date of LA Regimen is defined as follows for participants who prematurely discontinued study drug or complete study drug according to Study Drug Completion eCRF (i.e. participant answered “No” or “Yes” for “Did participant complete study drug dosing as specified per protocol” on Study Drug Completion form):

- the earliest date of last study day or ART restart day for participants who prematurely discontinued study or complete study, or

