7.7. Changes from Protocol-Specified Safety Analyses

No change from protocol-specified safety analyses is planned.

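### No table in the final-analysis SAP counts treatment-emergent SAEs through Week 26, the stated primary endpoint: one period can stop earlier (or later), the other runs to about Week 52

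*SAP*

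**What the plan says.** Protocol 8.1.2 gives the primary endpoint as "Incidence of treatment-emergent SAEs through Week 26", and SAP 7 repeats it: "the primary endpoint of this study is incidence of treatment-emergent SAEs through Week 26". Protocol 8.6.2 treats an AE as treatment-emergent if it "begins on or after the date of first dose of study drug up to the end of the protocol-defined follow-up period".

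SAP 7.1.5.1 has two limbs. An AE that leads to premature study drug discontinuation counts with no end date. Any other AE counts from the start of study drug up to a period-specific cut-off:

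- LA Regimen Period: onset "prior to the last exposure date of LA Regimen Period for the LA Regimen Period Analysis". SAP 3.8.1 sets that date at "the earliest date of last study day or ART restart day for participants who prematurely discontinued study or complete study". The matching safety set (SAP 3.1.4) requires the complete long-acting regimen.
- Whole Study Period: onset no later than the last exposure date. For anyone injected or infused this is the last study date: "Last Study Date is the latest clinic visit dates, and/or the laboratory visit dates, whichever is latest". The definition goes on to include follow-up visit dates.

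SAP 3 adds an exception to the LA cut-off: "For participants who did not restart ART on or before last study date or have missing ARV restart date, all data will be included". SAP 7.1.6 summarises SAEs in these two periods only and lists all SAEs and all deaths. SAP 7.7 states: "No change from protocol-specified safety analyses is planned".

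**The concern.** A primary endpoint with a fixed window needs a table with that window. Here the period nearest to Week 26 ends at an event, ART restart, that virologic failure triggers. Its length therefore depends on the participant's outcome. The other period continues for about 26 weeks beyond the endpoint. A reader of the final report could not take the primary endpoint from either table and would have to rebuild it from listings.

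Two further points make the result depend on programming choices. SAP 3 and SAP 7.1.5.1 disagree on which AEs enter the LA period for a participant with no recorded ART restart. Also, both cut-offs depend on the last attended visit, whereas the protocol's window runs to the end of follow-up. With about 20 participants in the Primary Cohort, moving one SAE in or out visibly changes the estimate.

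**Working it through.** **1. The windows side by side**

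| | Last onset counted | Participants |
|---|---|---|
| Primary endpoint | Week 26 (nominal Day 182) | any dose (Protocol 8.3.1.3) |
| LA Regimen table | day before the earlier of ART restart and last study date | complete regimen only |
| Whole Study table | last study date, nominally Week 52 | any dose |

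**2. Where an SAE lands** (second limb of SAP 7.1.5.1)

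| SAE | Endpoint | LA table | Whole Study table |
|---|---|---|---|
| Before Week 26, after early ART restart, still attending | in | out | in |
| Before Week 26, GS-2872 never given | in | out | in |
| After Week 26, ART restart later still or undated | out | in | in |
| Weeks 26 to 52, ART restarted at Week 26 | out | out | in |
| Before Week 26, after last visit, already back on ART | in | out | out |
| Before Week 26, after last visit, not back on ART | in | out by 7.1.5.1, in by Section 3 | out |

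The last two rows change if the event is recorded as leading to study drug discontinuation, because that limb has no end date. Protocol 5.3 foresees infusions that are permanently stopped, so the second row is possible.

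**3. Follow-up missing from the LA table after early restart**

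Restart at Week 12: 26 − 12 = 14 weeks, and 14/26 = 53.8%.

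More generally, suppose HIV-1 RNA ≥ 200 copies/mL is first seen at Week w, is confirmed 2 to 3 weeks later (Protocol 6.8.1), and ART restarts that day (an assumption). Restart day = 7w + 14 to 7w + 21. Days omitted = 182 − restart day. The restart day itself is also excluded, since onset must come before it.

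| w | Restart day | Days omitted of 182 | Share |
|---|---|---|---|
| 4 | 42–49 | 133–140 | 73–77% |
| 8 | 70–77 | 105–112 | 58–62% |
| 12 | 98–105 | 77–84 | 42–46% |
| 16 | 126–133 | 49–56 | 27–31% |
| 20 | 154–161 | 21–28 | 12–15% |

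In the other direction, a study completer with no restart date has an LA period that runs to the last study date, up to 52 − 26 = 26 weeks too long.

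**4. Events after the last visit**

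Protocol 6.5 lets the post-early-termination Day 180 contact be a phone call, and AEs are reviewed on it. The SAP does not say whether a call counts as a follow-up visit. Take early termination at Week 4 (Day 28), ART restarted, and no further scheduled visits attended. The 90-day visit falls on Day 28 + 90 = 118 and the 180-day call on Day 28 + 180 = 208. If the call is not a visit, an SAE starting on Days 119 to 182 lies inside the endpoint's window but outside both tables.

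**5. Effect of one SAE**

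The plan gives no precision for the SAE endpoint. Its Clopper-Pearson table for virologic failure at n = 20 (Protocol Table 8-1, SAP Table 1-1) applies to any proportion, and its limits reproduce:

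- 0/20: upper limit 1 − 0.025^(1/20) = 16.8%.
- 1/20: lower limit 1 − 0.975^(1/20) = 0.1%; upper limit, the 97.5% point of Beta(2, 19), = 24.9%.

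One SAE left out therefore turns 1/20 (5.0%, 0.1 to 24.9%) into 0/20 (0 to 16.8%). In an arm of 10 (20 randomised 1:1), 1/10 (0.3 to 44.5%) becomes 0/10 (0 to 30.8%).

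**The case against.** The strongest reply is that the LA period is the SAP's practical version of Week 26. All participants are to resume ART at Week 26, so for anyone without early failure or withdrawal the two nearly coincide. Stopping at ART restart is a defensible summary of time on the regimen, and a second table ignores restart. That stands as a reason to keep both tables. It does not supply the missing one.

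The reply also corrects several stronger readings that a reader might infer:

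- That SAEs in early failures are lost. They are not. Protocol 6.8.2 keeps these participants on study, so their later SAEs enter the Whole Study table and the SAE listing. What is missing is a Week 26 count that contains them.
- That every fatal SAE after the last visit drops out. The documents do not establish this. The SAP 3 exception would bring in a participant not back on ART. SAP 6.1.2 also allows study drug discontinuation for AE or death up to the Week 26 window, although dosing ends on Day 2, so the limb without an end date may apply. Post-termination clinic visits also extend the last study date.
- That the SAE rate is biased downward. Early restart removes events from the LA table and late or undated restart adds them, so the net direction is unknown.
- That the primary endpoint was never analysed as defined. SAP 2.2 reports the Week 26 primary analysis as already conducted, and its plan is not among the documents. Part of the SAP 1.2.2 text on the analysis periods is also redacted. SAP 3, however, states that there are two sets of analyses and defines both.

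Against SAP 7.7 the point is narrower than it first looks. For completers the last study date is the end of scheduled follow-up, so the Whole Study period departs from Protocol 8.6.2 only for events after the last visit.

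**Conclusion.** The point holds for this final-analysis SAP. Followed as written, it produces no table of treatment-emergent SAEs through Week 26. The LA table can be too short (54% of the window missing for a Week 12 restart, and 12 to 77% under the confirmation-interval assumption), too long, or missing a partly dosed participant. The Whole Study table adds Week 26 to 52 events. The clear gap in both is an SAE that starts after the last clinic, laboratory or follow-up visit in someone already back on ART and is not recorded as leading to discontinuation. For someone not back on ART, SAP 3 and SAP 3.8.1/7.1.5.1 contradict each other and must be reconciled.

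This is a should-fix. The endpoint is descriptive and all SAEs and deaths are listed, so the correct count can be recovered. How many events are affected cannot be known from the plan; the one-event contrast in 20 is an illustration.

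**What to change.** - In SAP 7.1.5.1 and 7.1.6, add a primary-endpoint table on the Safety Analysis Set: participants with an SAE (and, as secondary, any AE) starting from first dose through the Week 26 visit, or Day 182 if that visit is not attended. Count all reported events regardless of ART restart. Show beside it the number not followed to Week 26, because a fixed cut would otherwise treat unobserved participants as event-free.
- Keep the table that ends at ART restart as supportive.
- Reconcile the SAP 3 exception with SAP 3.8.1 and 7.1.5.1 for AEs, so that one rule covers participants with no restart or no restart date.
- Align the Whole Study cut-off with the protocol's end of follow-up, so that reported events and deaths after the last visit count. State whether follow-up phone calls extend the last study date.
- Record the changed treatment-emergent windows in SAP 7.7.

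The cost is SAP wording, one flag and one table. No new data are needed and sample size does not change. The reported SAE rate may come out slightly less favourable, by one participant in 20 in the illustration above.

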7.1.5.2. Incomplete Dates

If the onset date of the AE is incomplete and the AE stop date is not prior to the first dose date of study drug, then the month and year (or year alone if month is not recorded) of onset determine whether an AE is treatment emergent. The event is considered treatment emergent as follows:

- Participants who receive any injection or infusion drug: the AE onset date is the same as or after the month and year (or year) of the first dose date of study drug
- Participants who do not receive any injection or infusion:
 - The AE onset is the same as or after the month and year (or year) of the first dose date of study drug, and
 - The AE onset date is the same as or before the month and year (or year) of the last exposure date

An AE with completely missing onset and stop dates, or with the onset date missing and a stop date later than the first dose date of study drug, will be considered to be treatment emergent. In addition, an AE with the onset date missing and incomplete stop date with the same or later month and year (or year alone if month is not recorded) as the first dose date of study drug will be considered treatment emergent.

When calculating the duration of event or time to onset, the following imputation rule will be used:

Missing start month/day: Jan 1/first day of the month will be used unless this is before the start date of study drug; in this case the study drug start date will be used;

Missing stop month/day: Dec 31/last day of the month will be used, unless this is after the last study date; in this case the last study date will be used.

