3.1.4. Safety Analysis Set

The Safety Analysis Set is the primary analysis set for safety analyses. Safety analysis sets are defined for this study:

- The Safety Analysis Set includes all participants who were randomized and received at least 1 dose of study drug. This is the primary analysis set for safety analyses for whole study period. This analysis set will also be used to describe baseline information.
- The Safety Analysis Set for LA Regimen includes all randomized participants who have received at least one dose of the complete long acting study drug regimen (ie, SC LEN + GS-5423 and GS-2872). This is the primary analysis set for safety analyses for LA regimen period analysis.

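### The SAP's rule for partly dated AEs has no upper limit for injected or infused participants, which conflicts with the ART-restart limit on the LA Regimen Period; the SAP does not say which text governs.

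*SAP*

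**What the plan says.** SAP 7.1.5.1 gives each analysis period its own closing date. For the LA Regimen Period, a treatment-emergent AE must start "prior to the last exposure date of LA Regimen Period for the LA Regimen Period Analysis". SAP 3.8.1 defines that date as "the earliest date of last study day or ART restart day for participants who prematurely discontinued study or complete study", which for a participant who follows the plan is ART restart at Week 26. SAP Section 3 sets a similar boundary from the data side: AE data enter the LA-period analysis only if collected before that date.

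SAP 7.1.5.2 covers incomplete onset dates. If the AE did not stop before first dose, "then the month and year (or year alone if month is not recorded) of onset determine whether an AE is treatment emergent". For participants who received any injection or infusion, the single test is that "the AE onset date is the same as or after the month and year (or year) of the first dose date of study drug". Only for those who received neither does the section add a second condition: "The AE onset date is the same as or before the month and year (or year) of the last exposure date". The section does not distinguish the two analysis periods. It also classes as treatment-emergent an AE with onset and stop dates both missing, or with a missing onset and a stop date after first dose, again without a period limit. SAP 3.6.1 points to this section as the place where incomplete AE onset dates are handled.

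**The concern.** A complete onset date after ART restart takes an AE out of the LA period. Removing only the day of the month puts it back in, even when the remaining month and year leave no doubt that it began after restart. Counting an event as treatment-emergent is a sensible default when its period is uncertain. Here the period is known and the rule ignores it.

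The protocol's primary endpoint is treatment-emergent SAEs through Week 26, and treatment-emergent AEs through Week 26 are secondary. In this SAP the LA-period safety summary reports them. With about 20 participants in the Primary Cohort, one record is visible in the percentage. Two programmers working from the same SAP could produce different LA-period counts, and different treatment-emergent flags in the listings of SAP 7.1.6.

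**Working it through.** **Who falls in the uncapped branch.** SAP 3.1.4: "The Safety Analysis Set for LA Regimen includes all randomized participants who have received at least one dose of the complete long acting study drug". Membership thus requires SC LEN and both antibodies. Every member was therefore injected and infused, so the capped branch of 7.1.5.2 never applies in the LA-period analysis.

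**Why the gap is harmless in the other period.** SAP 3.8.1: "For participants who receive any injection or infusion, last exposure date is defined as last study date". For these participants whole-study exposure ends when the study ends, so no upper limit is needed. The rule fits the Whole Study Period and appears not to have been adapted to the earlier LA limit.

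**Worked dates (assumed).** Day 1 is 15 Mar 2022. ART restart on Day 182 is Day 1 + 181 days = 12 Sep 2022. The last visit on Day 364 is Day 1 + 363 days = 13 Mar 2023.

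| Recorded onset | Rule that applies | LA-period treatment-emergent as written | With a month/year cap at ART restart |
|---|---|---|---|
| 15 Nov 2022 (complete) | 7.1.5.1 | No | No |
| Nov 2022 (day missing) | 7.1.5.2 | Yes | No |
| 2023 (year only) | 7.1.5.2 | Yes | No |
| Sep 2022 (restart month) | 7.1.5.2 | Yes | Yes |
| Jun 2022 (day missing) | 7.1.5.2 | Yes | Yes |

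The first two rows show the conflict. The last two show that a cap leaves ambiguous and clearly in-period events where they are.

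**How much of the calendar is exposed.** In the example, follow-up touches 13 calendar months (Mar 2022 to Mar 2023), and 6 of them (Oct to Mar) lie wholly after the restart month: 6/13 = 46%. Over every possible Day 1 in a year, the count is 5 to 7 of 12 or 13 months, also 46% on average. This is a share of calendar months, not of AEs.

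**Size of one misassigned SAE.** The plan states no figure for this point. Its Clopper-Pearson limits for 20 participants (SAP Table 1-1, written for virologic failure) reproduce: 0/20 has an upper limit of 1 − 0.025^(1/20) = 16.8%, and 1/20 has limits 0.1% to 24.9%. Applied to SAEs:

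- 20 participants: 0/20 = 0% (95% CI 0 to 16.8) becomes 1/20 = 5% (0.1 to 24.9), a change of 5 points.
- An assumed group of 10 (1:1 split of 20): 0/10 = 0% (0 to 30.8) becomes 1/10 = 10% (0.3 to 44.5), a change of 10 points.

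**The case against.** The best reply is that SAP Section 3 already settles the matter. An AE that began in a month after restart cannot have been collected before restart, so the Section 3 cut removes it whatever 7.1.5.2 says. On this reading, Section 3 and 7.1.5.1 fix the period, and 7.1.5.2 only decides whether an event began on or after first dose.

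Part of this stands. If the Section 3 cut is applied first, the example is excluded and there is no miscount. But 7.1.5.2 cannot be read as a start-date rule only, because it writes an upper limit for oral-only participants. Section 3.6.1 names it as the rule for incomplete onsets, and nothing ranks it below Section 3. Section 3 also gives no method for partial dates, and the imputation at the end of 7.1.5.2 serves only event duration and time to onset.

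Other points lower the stakes, and they stand. SAEs go to the sponsor within 24 hours of the investigator's knowledge (protocol 7.4.1.1) and are reconciled with the safety database before data finalization (SAP 7.1.4). Source records must hold AE start and end dates (protocol 9.1.6). An SAE with a partial onset date is therefore the least likely case. All AEs and SAEs are listed with their treatment-emergent status, so a misplaced record could be seen by eye. No formal safety stopping rule depends on the count.

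**Conclusion.** The point holds as a conflict among SAP Section 3, 7.1.5.1 and 7.1.5.2. It is minor and worth correcting because the correction is nearly free. For it to affect a count, three things must coincide: an AE with an incomplete or missing onset date, information placing that onset after a recorded ART restart, and a programmer who applies 7.1.5.2 without the Section 3 cut. One such SAE is worth 5 points in 20 participants, or 10 in an assumed group of 10.

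A reader might infer three stronger things that the documents do not support:

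- **That the LA-period count will be wrong.** Section 3 gives a programmer a textual basis for the correct result, so a miscount is possible but not certain.
- **That the primary analysis is affected.** SAP 2.2 reports that analysis as already conducted. This SAP governs the final analysis (SAP 2.4), so the output at issue is its LA-period summary.
- **That about half of partly dated AEs would be misplaced, because about half of follow-up comes after Week 26.** That needs evenly spread onsets. All dosing is on Days 1 and 2, and scheduled AE review is much denser before Week 26 than after it, when only Weeks 38 and 52 remain. Nothing in the documents supports an even spread.

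**What to change.** State the partial-date rule in SAP 7.1.5.2 separately by period.

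- **LA Regimen Period Analysis:** after the existing lower limit, add *and the month and year (or year) of onset is the same as or before that of the last exposure date of LA regimen*. Events in the restart month stay treatment-emergent, so real ambiguity is still resolved by inclusion.
- **Completely missing onset dates:** the added limit does not reach these. State that they are subject to the Section 3 LA-period cut where the collected information places them after ART restart.
- **Whole Study Period Analysis:** keep the current rule.
- **AEs leading to premature discontinuation of study drug (first bullet of 7.1.5.1):** leave unchanged.

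The cost is a short addition to the text and one condition in the code. If the SAP is already final, its introduction allows the change to be documented in the CSR.
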